Is life threatening																		
Results in persistent or significant disability or incapacity																		
Requires hospitalization or continuation of existing hospitalization																		
Important medical event																		
Total																		

* 1. Not related 2.unlikely to be related 3.Possible 4. Probable 5. Most probably 6. Insufficient data to assess

** 1. Results in death 2. Is life threatening 3. Results in persistent or significant disability or incapacity 4. Requires hospitalization or continuation of existing hospitalization 5. Important medical event (may not result in death but may jeopardise subject)

*** As defined in the protocol list of solicited adverse events

SOP VEL 1/1:	Statistical Analysis Plan	Page 46 of 61
Sep 2012		

Phase II/III	WHO Measles Aerosol Vaccine	Protocol
Clinical Trial	Project	WHO/MAP/IN/002

Table 14.0.4: Characteristics of duration of adverse event separately for severity, causality and by administered intervention

								Milo	d							Moderate									Severe																						
	I	Poss	sible	e	Pr	oba	ble		l Pr	Mos obal	t bly		Not	Rela	ated		Pos	sible	9		Pro	obab	le	Р	Mo Prob	ost ably		I	Not 1	Relate	ed		Ро	ssible			Prob	able	;	Most Probably				Not Related			
Adverse Event	AER		\mathbf{SC}		AER		\mathbf{SC}		AER		SC		AER	C C	n n	A E D	AER			AER			AER		sc		AER		SC		AER		SC		AER		sc	2	AER		SC		AER		SC		
	Mean	uc		SU	Mean	SD	Mean	Mean	SD	Mean	SD	Vean	SD	Mean	8D	Mean	SD	Mean	SD	Mean	CIC.	Mean	л	Mean	SD	N	20	Mean	SD	Mean	SD	Mean	SD	Mean	SD	Mean	SD	Mean	ßD	Mean	SD	Mean	SD	Mean	SD	Mean	SD
Anorexia																																							\square								
Conjunctivitis																																							\square								
Coryza																																															
Cough																																							\square								
Crying																																							\square								
Diarrhoea																																						1	\square								
Difficulty																																							\square								
Fever																																						1	\square								
Irritability																																							\square								
Local																																							\square								
Malaise																																						1	\square		1						
Rash																																						1	\square		1						
Seizure																																						1	\square								
Shivering																																						1	\square								
Vomit																	1												1									1	\square		i T						
Wheeze																1	1		1														1					\mathbf{T}	\square		i						

SOP VEL 1/1:	Statistical Analysis Plan	Page 47 of 61
Sep 2012		

15.0 Trial Termination:

The trial will be terminated according to the stopping rules determined by the DSMB. The criterion for termination is the occurrence of the single serious adverse event or encephalitis/encephalopathy in one or more subjects which is deemed to be most probably related to the Aerosol vaccine.

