8.6.3 Sample processing

8.6.3.1 Laboratory measurement of immunogenicity

- All serum samples will be tested by Enzygnost Anti-measles-virus/IgG ELISA (Dade-Behring, Marburg, Germany) (SOP HPA 5/1 and SOP HPA 6/1).
- In addition, all specimens with Enzygnost optical density readings <0.1 will be tested by plaque reduction neutralization test (SOP HPA 7/1).

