9.2 Secondary outcomes

For all infants:

- Geometric mean titres, pre-vaccination and at day 91;
- Seroconversion (defined as a change from Enzygost OD <0.1 to OD \ge 0.1 or PRNT from <120 to \ge 120 mIU/mL) measured in paired samples from day 0 and day 91;
- As covariates for inclusion in multivariable analyses: age; sex; day 0 antibody titre; study site; crying when vaccine given (aerosol arm only); presence of respiratory tract symptoms at time of vaccination (aerosol arm only). In addition, random subsets of 80 infants each with OD 0.1-0.2 and OD>0.2 at day 91 will be assessed for PRNT antibody concentrations to determine the relationship between PRNT and Enzygost optical densities/concentrations and validate the use of the cut-off of 0.1 for PRNT testing.

For infants in the day 28 blood sample subset or the day 364 blood sample subset:

- Geometric mean titres to describe evolution of antibody response at days 0, 28, 91, 364;
- Seropositivity at 364 days in infants with antibody titre \geq 120 mIU/ml at day 91.

10 Assessment of Safety

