Purpose:

This document describes principles and procedures for statistical aspects of the randomized controlled trial protocol. The document is referred to as the Statistical Analysis Plan (SAP). The contents of the SAP are in accordance with the guidelines of the International Conference on Harmonisation (ICH) of Technical Requirements for Registration of Pharmaceuticals for Human Use and the Consolidated Reporting Standards for Trials extension to non-inferiority trials (1).

3.0 Policy and Scope:

The SAP is applicable to procedures for the statistical analysis of data generated during the MAP trial to be undertaken at Vadu, Maharashtra, India. The planned analyses are outlined in the protocol WHO/MAP/IND/002 August 2008, Section 11.

4.0 General Responsibilities:

The Principal Statistician is responsible for carrying out the statistical analysis of the clinical data according to the protocol and this SAP and to ensure that other responsible staff members perform their duties according to this SAP.

5.0 Materials and Equipments:

Hardware:

- 1. Desktop personal computers with MS Windows Network
- 2. Laptops with MS Windows Network

SOP VEL 1/1:	Statistical Analysis Plan	Page 3 of 61
September 11, 2012		

Software:

1.	Website development	:	XAMPP 1.6.6a (PHP 5.2.5, MySQL 5.0.51a, Apache), Apache friends group, Germany
2.	Statistical Analyses	:	SAS 9.1, SAS Institute Inc., Cary, NC, USA
3.	Audit trail software		Promasys 6.0, PROMASYS BV, Leiden, The Netherlands

6.0 Assessment of Outcomes:

The planned primary and secondary outcomes, and timing of their measurement, are outlined below.

6.11mmunogenicity:

6.1.1 Primary Outcome:

Measles seropositivity at day 91 post vaccination. This is defined as an optical density value (OD) >=0.1 or a plaque reduction neutralisation test (PRNT) result of >=120mIU/ml. Samples with an OD<0.1 at day 91 will be tested by PRNT as well as all samples from the Vadu study site.

6.1.2 Secondary Outcomes:

For all infants:

- Geometric mean ODs, pre-vaccination and at day 91;
- Seroconversion (defined as a change from Enzygnost enzyme-linked immunosorbent assay (ELISA) OD <0.1 to OD >=0.1 (unless PRNT results are available, in which case it is a change from PRNT from <120 to >= 120 mIU/ml) measured in paired samples from day 0 and day 91

For infants from Vadu in 28 and 364 days subsets:

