12.1. Efficacy Analyses: Immunogenicity

 Table 12.1.1A: Results of ELISA and PRNT, by study group, per-protocol analysis

	Baseline		Day	y 91
	AER	SC	AER	SC
	n=	n=	n=	n=
ELISA result (optical density)				
Median				
Interquartile range				
Min – Max				
Geometric mean titre				
95% CI	n=	n=	n=	n=
PRNT result (mIU/ml)				
Median				
Interquartile range				
Min – Max				
Geometric mean titre				
95% CI				

Legend:

AER – aerosol; SC - subcutaneous

For PRNT titre, includes subjects whose OD values are < 0.1 and all from Vadu site

SOP VEL 1/1:	Statistical Analysis Plan	Page 24 of 61
September 11, 2012		

	Baseline		Day 91	
	AER	SC	AER	SC
	n=	n=	n=	n=
ELISA result (optical density)				
Median				
Interquartile range				
Min – Max				
Geometric mean titre				
95% CI	n=	n=	n=	n=
PRNT result (mIU/ml)				
Median				
Interquartile range				
Min – Max				
Geometric mean titre				
95% CI				

Table 12.1.1B: Results of ELISA and PRNT, by study group, ITT analysis

Note: For PRN titre, the subjects whose OD values are < 0.1 and from Vadu site

12.1.2: Day 91 ELISA and PRNT results

Table 12.1.2A: Aerosol Group

	PRNT <120	PRNT >=120	PRNT not done	Total
Day 91 ELISA <0.1				
Day 91 ELISA >=0.1				
Day 91 ELISA Not done				
Total				

Legend:

Boxes highlighted in yellow represent results classified as seropositive at day 91

Phase II/III	WHO Measles Aerosol Vaccine	Protocol
Clinical Trial	Project	WHO/MAP/IN/002

Table 12.1.2B: Subcutaneous Group

	PRNT <120	PRNT >=120	PRNT not done	Total
Day 91 ELISA <0.1				
Day 91 ELISA >=0.1				
Day 91 ELISA Not done				
Total				

Legend:

Boxes highlighted in yellow represent results classified as seropositive at day 91

Table 12.1.3: Measles seropositive at day 91 post-vaccination (all infants) and difference in positivity between study arms

	AER n/N	AER%, 95% CI	SC n/N	SC%, 95% CI	Difference (AER- SC), 95% CI*
Seropositive at day 91					

Legend:

AER – aerosol; SC – subcutaneous;

* This difference is used to interpret non-inferiority, estimated by Wilson score method (5) (6).

Table 12.1.4A: Comparison of serological outcomes, by study group and time of sample collection: **Per Protocol cohort**

	AER		SC		Difference	
Time point	n	%	n	%	(AER-SC) 95% CI	
Day 0, seropositive						
Day 91, seropositive						
Day 91, seroconversion						

Legend:

AER – aerosol; SC - subcutaneous

Phase II/III	WHO Measles Aerosol Vaccine	Protocol
Clinical Trial	Project	WHO/MAP/IN/002

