(OD<0.1)				

Table 12.1.0: Geometric mean titles, pre-vaccination and at day 91 101 an infant	Table 12.1.8:	Geometric mean	titres, pre-v	vaccination and	l at dav	y 91 fc	or all infants
---	---------------	----------------	---------------	-----------------	----------	---------	----------------

12.2 Secondary End Point (For infants from Vadu in 28 and 364 days subset): ITT Cohort

12.2.1*Analysis:* Geometric mean titres and ODs at days 0, 28, 91 and 364 to describe evolution of antibody response;

Table 12.2.1.1A: Descriptive statistics of infants age 9 to 11.99 months at vaccination and change in ELISA titer for subset of subjects at Vadu followed to day 364

	Baseline		Day	Day 28 Da		y 91	Day 364	
	AER	SC	AER	SC	AER	SC	AER	SC
	n=	n=	n=	n=	n=	n=	n=	n=
ELISA Titer: (\triangle OD)								
Median								
Min – Max								
GMT								
95% CI								

Table 12.2.1.1B: Descriptive statistics of infants age 9 to 11.99 months at vaccination and change in PRN titer for subset of subjects at Vadu followed to day 364

	Bas	Baseline		y 28	Day	⁷ 91 Day		y 364	
	AER	SC	AER	SC	AER	SC	AER	SC	
	n=	n=	n=	n=	n=	n=	n=	n=	
PRN Titer: (mIU/ml)									
Min – Max									
GMT									
95% CI									

SOP VEL 1/1:	Statistical Analysis Plan	Page 29 of 61
September 11, 2012		

Phase II/III	WHO Measles Aerosol Vaccine	Protocol
Clinical Trial	Project	WHO/MAP/IN/002

Table 12.2.1.2: Geometric mean titres, pre-vaccination and at days 28, 91, 364 for
infants in the Vadu subset

GMTs							
	AER			SC	Ratio	95% CI	
	n	GMTs	n	GMTs	AER/SC		
28 days subset							
Day 0 OD							
Day 28 OD							
Day 91 OD							
Day0 PRNT							
Day 28 PRNT							
Day 91 PRNT							
364 days subset							
Day 0 OD							
Day 91 OD							
Day 364 OD							
Day 0 PRNT							
Day 91 PRNT							
Day 364 PRNT							

12.2.1.3: Seropositivity at 364 days in infants with PRNT \geq 120 mIU/ml at day 91

12.2.1.3A: Aerosol group

			Day 364	
1	PRNT	<120	>=120	Total
y 9.	<120			
Day	>=120			
	Total			

12.2.1.3B: Subcutnaeous group

			Day 364	
1	PRNT	<120	>=120	Total
y 9.	<120			
Day	>=120			
	Total			

SOP VEL 1/1:	Statistical Analysis Plan	Page 30 of 61
September 11, 2012		

Phase II/III	WHO Measles Aerosol Vaccine	Protocol
Clinical Trial	Project	WHO/MAP/IN/002

12.2.1.4: Seropositivity at days 0, 28, 91 and 364 and changes betw	een these time
points	

Table 12.2.1.4.1:	Measles	seropositivity at	days () 28	91	and 364.
1 auto 12.2.1.7.1.	Medsies	scropositivity at	uayov	J, 20,	1	ana 50 4 .

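### PRNT geometric means in SAP Tables 12.1.1A/B come from a pool enriched with poor responders, and two Table 12.1.8 ratios condition on the day-91 outcome

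*Supplement*

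**What the plan says.** SAP 6.1.1 sets who gets a PRNT: "Samples with an OD<0.1 at day 91 will be tested by PRNT as well as all samples from the Vadu study site". Protocol 8.6.3.1 states the low-OD rule without naming a day: "all specimens with Enzygnost optical density readings <0.1 will be tested by plaque reduction neutralization test". Protocol 9.2 adds a validation sample: "random subsets of 80 infants each with OD 0.1-0.2 and OD>0.2 at day 91 will be assessed for PRNT antibody concentrations".

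SAP Tables 12.1.1A (per protocol) and 12.1.1B (ITT) give the PRNT median, interquartile range, range, GMT and 95% CI by arm, at baseline and day 91. The legend of 12.1.1A reads "For PRNT titre, includes subjects whose OD values are < 0.1 and all from Vadu site". The note to 12.1.1B reads "For PRN titre, the subjects whose OD values are < 0.1 and from Vadu site", which could also be taken to mean only children who meet both conditions. SAP 11.12.1 specifies a log10 transformation and mentions no weights. Neither table has a ratio column.

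Arm ratios with 95% CIs are in Table 12.1.8, whose title covers all infants. Its rows are OD in everyone (day 0 and day 91), day-91 OD among those above 0.1, and day-91 PRNT among those below 0.1. The SAP's all-infant secondary outcome is on the OD scale: "Geometric mean ODs, pre-vaccination and at day 91". Table 12.2.1.2 ("Geometric mean titres, pre-vaccination and at days 28, 91, 364 for" the Vadu subset) plans PRNT GMTs and ratios in randomly drawn Vadu children.

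For seroconversion, SAP 6.1.2 uses a change in OD "unless PRNT results are available, in which case it is a change from PRNT from <120 to >= 120 mIU/ml".

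**The concern.** Outside Vadu a day-91 PRNT exists because the response was poor. Adding those children to a complete Vadu sample gives a mean that belongs to no defined population, and its confidence interval is centred on the wrong value. The legend discloses the selection but does not correct it. A reader looking for the neutralising titre after aerosol or subcutaneous vaccine would take the printed GMTs at face value and could divide one by the other.

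The conditioned rows of Table 12.1.8 have a different fault. OD at day 91 is itself a result of vaccination, so comparing arms within an OD stratum is not a randomised comparison. If one route produces more low responders, its low-OD group differs in composition from the other arm's.

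The same selective testing reaches seroconversion, because PRNT decides where it exists and its existence depends on site and on OD.

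**Working it through.** **Inputs from the documents.** SD of log10 PRNT 0.43 and 100 children per arm in the subsets (SAP 8.1); cut-off 120 mIU/ml; assumed seropositivity 90% in both arms; 800 evaluable per arm.

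**Assumptions not in the documents.**
- Vadu share v: 24.7% (661/2677, protocol Table 5), 27.6% (552/2000, if the SAP 7.1 list of 552 is the Vadu total) or 35%.
- Share q with OD <0.1: 10% to 20% when the arms are equal, and 5% to 10% in the subcutaneous arm when they differ.
- Correlation r of log OD with log PRNT: 0.6 to 0.95.
- Vadu titres resemble those elsewhere, and log10 PRNT is normal.

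**The plan's own PRNT figure.** Detectable ratio with 100 per arm: 10^(0.43 × (1.96 + 0.842) × sqrt(2/100)) = 1.48. The stated figure of less than 1.5-fold reproduces.

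**Level of the pooled GMT, equal arms.**
- All-infant mean log10 titre m = log10(120) + 1.2816 × 0.43 = 2.630, so the GMT is 427.
- Mean among low-OD children = m − r × 0.43 × φ(z)/q, where z is the normal deviate cutting off q. For q = 0.10 and r = 0.8: 2.630 − 0.8 × 0.43 × 1.755 = 2.027, GMT 106.
- Weight of the extra low-OD children in the pool = (1−v)q / [v + (1−v)q]. For v = 0.276: 0.0724/0.3484 = 0.208.
- Pooled mean = 2.630 − 0.604 × 0.208 = 2.505, GMT 320, which is 25% too low. The low-OD share in the pool is 0.10/0.3484 = 29% instead of 10%.
- Mildest case (v = 0.35, q = 0.10, r = 0.6): shift −0.453 × 0.157 = −0.071, or −15%.
- Most severe case (v = 0.247, q = 0.20, r = 0.95): shift −0.572 × 0.379 = −0.217, or −39%.

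A simulation with one million children per arm gives the same values. A smaller Vadu share makes the bias larger.

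**Ratios.** With identical arms, every ratio stays at 1.00. With 85% (aerosol) against 95% (subcutaneous) seropositive, the all-infant GMTs are 335 and 612, a ratio of 0.55. For v = 0.276, r = 0.8 and 10% low OD in the subcutaneous arm (21% then follows in the aerosol arm):

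| Sample | Aerosol / subcutaneous | Range over all settings |
|---|---|---|
| All infants | 0.55 | 0.55 |
| Low OD plus Vadu (12.1.1A/B, by division) | 228/458 = 0.50 | 0.45–0.52 |
| OD <0.1 only (PRNT row of 12.1.8) | 0.75 | 0.65–0.86 |
| Vadu only | 0.55 | 0.55 |

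The two selected samples err in opposite directions.

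**Seroconversion.** Take two children who are negative on both assays at day 0 and have day-91 OD ≥0.1. The Vadu child also has a day-91 PRNT. If it is below 120, that child is seropositive under SAP 6.1.1 but not seroconverted under 6.1.2. The child outside Vadu normally has no day-91 PRNT and is judged on OD. The same underlying response can be classified differently by site.

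**The case against.** The strongest reply is that the plan already contains valid comparisons. The all-infant geometric-mean outcome is OD, reported with a ratio in everyone. Table 12.2.1.2 gives PRNT ratios at day 91 in children chosen without regard to OD, and the SAP's only power statement on titres refers to those subsets. The selected samples are labelled, and the primary analysis uses none of these GMTs. All of this stands, and it limits the point to secondary results. It does not make the pooled GMTs or the conditioned ratios interpretable.

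A reader might infer that the plan reports an exaggerated PRNT ratio on the low-OD-plus-Vadu pool. It does not: that ratio arises only if someone divides the printed GMTs. The PRNT ratio planned in Table 12.1.8 is pulled towards 1, and equal arms produce no distortion at all.

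A larger bias can also be produced. If all responders sit at 1000 and all low-OD children at 50 mIU/ml, 10% low OD gives 423 against 741, or 43% too low. But that mixture alone uses an SD of 1.3 × sqrt(0.1 × 0.9) = 0.39 of the 0.43 the SAP states for the subcutaneous arm, so it is not relied on here.

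On seroconversion, Table 12.1.7 marks the qualifying cells by colour, which is not visible in the text reviewed. Those cells may settle some cases, but the wording of 6.1.1 and 6.1.2 still differs.

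**Conclusion.** The point holds for planned secondary summaries. The day-91 PRNT GMTs in Tables 12.1.1A/B are biased low as all-infant values, by about 15% to 39% over the range tried. The direction was the same in every setting; the size rests on the assumed low-OD share, correlation and Vadu share. The OD >0.1 and PRNT (OD <0.1) ratios in Table 12.1.8 condition on the outcome and do not fit the table's title. The PRNT one moved a true 0.55 to between 0.65 and 0.86. The size of any error in the OD >0.1 ratio was not calculated.

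The documents do not support a claim that the trial's titre comparison as a whole is invalid, or that the non-inferiority conclusion is at risk. The seroconversion inconsistency is a separate, smaller matter of definition, and its frequency cannot be estimated from the documents.

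**What to change.** 1. **Tables 12.1.1A/B.** Compute the PRNT summaries from all Vadu children only and label them as Vadu estimates. Add the day-91 aerosol/subcutaneous PRNT ratio with its CI on that sample. This also removes the ambiguity in the 12.1.1B note.
2. **Table 12.1.8.** Remove the ratio and CI from the OD >0.1 and PRNT (OD <0.1) rows, leaving them as descriptive counts and GMTs. Keep the OD ratio in everyone as the all-infant comparison.
3. **SAP 6.1.2.** Define seroconversion at every site as a change from negative to positive on the primary composite (OD ≥0.1 or PRNT ≥120 mIU/ml). This needs PRNT on day-0 samples with OD <0.1, which protocol 8.6.3.1 already covers. Reconcile SAP 6.1.1, 6.1.2 and Table 12.1.7 with it.

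The cost is SAP wording and table programming, with no new samples for Vadu. With v = 0.276, about 0.276 × 800 = 221 children per arm remain, against 0.348 × 800 = 279 in the pool. At SD 0.43 the 95% CI for the ratio is then a factor of 10^(1.96 × 0.43 × sqrt(2/221)) = 1.20 either way, against 1.18 for 279 per arm at the same SD. A Vadu estimate speaks for other sites only if titres there are similar. Weighting with the protocol's validation sample is possible but optional: that sample is not stated per arm and is not named in the legends.

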When a unique study ID has been confirmed the person clicks the 'Randomization' button. The next screen gives the allocation as either, 'AEROSOL' or 'SUBCUTANEOUS'. The system records, in a separate database, the details of study site, child's names, Subject ID number, allocation, date and time of randomization. The randomization database will be maintained in Access as backend. This database will be maintained at the CDMC and the backup will be maintained at the backup server which is kept at the Pharmacology Department Museum (old name: Booshnam Moses Computing Center) (Refer SOP Randomization, No: 05 / 02).

SOP VEL 1/1:	Statistical Analysis Plan	Page 5 of 61	
September 11, 2012			

7.3 Blinding of Laboratory Staff:

Staff at the study sites and participants' parents will know which treatment has been given. To minimize bias in the assessment of immunogenicity outcomes, laboratory staff will not know the treatment allocation or the order of specimens that they will analyze.

In order to blind laboratory staff to the specimen collection time (day 0, day 28 day 91 or day 364) for the subjects, a single digit random number will be generated and concatenated with the subject ID. This is called the Lab Code. Thus a subject will have a unique Lab Code of 5 digits.

The laboratory will be provided with lists of 22 pairs (day 0 and day 91) of specimen Lab Codes, which will be randomly ordered. Similarly, for the specimens of children who will be followed up at day 28 and day 364, the laboratory will be provided with lists of randomly ordered Lab Codes.

8.0 Sample size:

8.1 Immunogenicity:

The sample size for the primary outcome is determined using the confidence interval (CI) approach, considering where the CI for the treatment effect lies with respect to a pre-specified margin of non-inferiority and the null effect (1).

Total to be enrolled, 2000. This number was based on the following assumptions:

- Significance 2.5%, one sided for non-inferiority, 5% for two sided superiority;
- Non-inferiority margin 5%;
- Power for non-inferiority 90% if true seropositivity is 90% in both arms;
- 20% loss to follow up by day 91, leaving 1600 available for primary analysis.

Sample size for immunogenicity subset:

Those selected for additional testing at day 28 or at day 364 will have ELISA and PRNT test results at these time points as well as at day 0 and 91.

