The sample size will be 100 in each arm at each of day 28 and day 364. Based on the estimated variability (Standard deviation) of post subcutaneous vaccination PRNT results of 0.43 on a \log_{10} scale ([name], Health Protection Agency London, personal communication) differences of <1.5 fold in geometric mean titres between aerosol and subcutaneous groups at each time point and between each time point would be able to be detected at a 5% significance level with 80% power.

8.2 Safety:

To estimate proportions with AE in Aerosol and Subcutaneous groups, the sample sizes above give acceptable precision.

SOP VEL 1/1:	Statistical Analysis Plan	Page 6 of 61
September 11, 2012		

Phase II/III	WHO Measles Aerosol Vaccine	Protocol
Clinical Trial	Project	WHO/MAP/IN/002

Table 8.2.1: Range of Precision with	Different Leve	els of Proportions	Experiencing
Event and Numbers of Participants.			

Observed	95% confidence intervals	
proportions	N=800	N=1000
0%	0.00 - 0.46%	0.00-0.37%
1%	0.43-1.96%	0.48-1.83%
2%	1.15-3.23%	1.26-3.07%
5%	3.60-6.75%	3.73-6.54%

The table shows that, if no reactions are observed, the upper 95% confidence interval with a sample size of 1000 is 0.37%, or 1 in 270.

9.0 Data Management and Pre-analysis Statistical Review:

9.1 Data Management:

The data management plan has been developed by the CDMC, Dept., of Biostatistics, Christian Medical College, Vellore. For more details refer to SOP 04/02 Clinical Data Management.

9.1.1 Data Quality Control, Query management and Quality Assurance:

Please refer SOPs Query Generation and Resolution (15/02) and Quality control and Quality assurance (16/02) for details.

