Baseline: Age in months, sex, usual health care provider, heart rate, respiratory rate, temperature, height for age, weight for age, any abnormality discovered on systemic examination, pre existing medical conditions (Table 11.12.6.1B)

Others: Observations during vaccination (Table 11.12.6.1D)

The distribution of the baseline covariates by study arm will be described, but not formally tested as randomization will have ensured that any differences are chance differences. For the main comparison of the study arms adjustment for these covariates is not necessary. To investigate the effect of these covariates on study end-points multivariable logistic regression (for binary end points) or normal errors regression (on logged antibody levels) will be performed. Study arm will be included in these analyses and interactions examined as given in section 11.11.

11.10 Sub-group analyses:

No sub group analyses have been planned.

11.11 Interactions with study arm:

Potential interactions will be examined for the following co-variates: sex, age, crying during measles vaccination, and acute respiratory infection.

11.12 Descriptive Analyses:

11.12.1 Distributions of continuous variables and any agreed transformations:

Mean, standard deviation, median, and interquartile range will be generated for continuous variables. The PRNT values will be doubled if the value is >20,000. The PRNT values will be \log_{10} transformed for further analyses such as GMT and 95% CI. Results at the lower limit of the assay will be assigned a value of 10. OD values will also be \log_{10} transformed to calculate geometric means and perform regression. Any OD results of <0.01 will be assigned a value of 0.005 prior to \log_{10} transformation.

11.12.2 Distributions of binary and categorical variables:

Frequency distributions will be shown for binary and categorical variables. The categories will be checked against the Annotated CRF.

11.12.3 Outliers:

For \log_{10} PRNT values, checks for outliers will be performed prior to the statistical analysis as part of the data checking. The outliers will also be examined using standardized residuals >3 when looking at \log_{10} PRNT values.

SOP VEL 1/1:
September 11, 2012

Phase II/III	WHO Measles Aerosol Vaccine	Protocol
Clinical Trial	Project	WHO/MAP/IN/002

11.12.4 Flow of Numbers:

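### SAP Tables 12.2.1.2 and 12.1.8: the arm GMT ratios are crude, and the plan never joins its log-antibody regression to the day-0 value in a baseline-adjusted ratio

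*Supplement*

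**What the plan says.** **The comparison tables.** SAP Table 12.2.1.2 ("Geometric mean titres, pre-vaccination and at days 28, 91, 364", infants in the Vadu subset) has columns for n and GMT in each arm, the AER/SC ratio and its 95% CI. The 28-day subset has rows for days 0, 28 and 91, and the 364-day subset has rows for days 0, 91 and 364, each for OD and PRNT. Table 12.1.8 gives the same kind of ratio for all infants at days 0 and 91. Neither table names a model or a covariate.

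**Day-0 data.** SAP 8.1 says that children selected for the extra bleeds "will have ELISA and PRNT test results at these time points as well as at day 0 and 91". Outside Vadu, PRNT coverage is narrower. SAP 6.1.1: "Samples with an OD<0.1 at day 91 will be tested by PRNT as well as all samples from the Vadu study site".

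**The regression.** SAP 11.9 plans normal-errors regression on logged antibody levels with study arm in the model. Its purpose is to examine what the covariates do to the endpoints. Its baseline list begins "Baseline: Age in months, sex, usual health care provider, heart rate, respiratory rate, temperature, height for age, weight for age" and goes on to examination findings and pre-existing conditions. Day-0 antibody is not in it. The section also says that the main arm comparison need not be adjusted for the covariates it lists.

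**Day-0 titre as a covariate.** It is listed for multivariable analyses in SAP 12.3 and protocol 9.2, and protocol 12.1.2 names pre-vaccination titre among the factors of interest. SAP 12.3 is a risk-factor section, and its only table models seronegativity within the aerosol arm.

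**The concern.** Antibody still present at nine to twelve months may relate to the level after vaccination. If it does, a chance difference between arms at day 0 carries through in part to the ratios at days 28, 91 and 364, and variation that a baseline covariate would explain stays in the confidence interval. The subsets have only about 100 children per arm, so this is where an imbalance or lost precision would show most.

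The plan holds both ingredients of the remedy in different places, and no output brings them together. The SAP 11.9 model contains study arm but not day-0 titre. The SAP 12.3 table contains day-0 titre but only one arm, so it cannot produce an arm ratio. A statistician following the SAP could report crude ratios only, or could choose an adjusted model after seeing the data. Neither course departs from the text.

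**Working it through.** **Inputs, all from SAP 8.1**
- Subset size: "The sample size will be 100 in each arm at each of day 28 and day 364".
- Spread: a standard deviation for "post subcutaneous vaccination PRNT results of 0.43 on a" log10 scale.
- Target: "differences of <1.5 fold in geometric mean titres between aerosol and subcutaneous groups at each time point and between each time point", at the 5% level (taken as two-sided) with 80% power.
- Correlation r between log10 day-0 and log10 post-vaccination values: **not given**. Assumed range 0 to 0.7.

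**Step 1. Reproduce the plan's figure (unadjusted, at one time point).**
Detectable log10 difference = (1.960 + 0.842) × 0.43 × √(2/100) = 0.1704, and 10^0.1704 = 1.48-fold. This agrees with the stated figure of less than 1.5-fold. Conversely, power for a true 1.5-fold ratio is 82.5% with 100 per arm, and 94 per arm would give 80%. The plan's claim at a single time point is therefore met by the crude comparison.

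**Step 2. Adjust for the child's own day-0 value.**
In a linear model with the day-0 value as covariate, the residual SD is 0.43 × √(1 − r²). Detectable fold = 10^[(1.960 + 0.842) × 0.43 × √(1 − r²) × √(2/100)].

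| Assumed r | Residual SD | Detectable fold (80% power) | Power for 1.5-fold | CI narrower on log scale by |
|---|---|---|---|---|
| 0 | 0.430 | 1.48 | 82.5% | 0% |
| 0.1 | 0.428 | 1.48 | 82.9% | 0.5% |
| 0.2 | 0.421 | 1.47 | 84.0% | 2% |
| 0.3 | 0.410 | 1.45 | 85.9% | 5% |
| 0.5 | 0.372 | 1.40 | 91.7% | 13% |
| 0.7 | 0.307 | 1.32 | 98.2% | 29% |

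**Step 3. Effect of a chance day-0 imbalance on the crude ratio.**
The shift in the later log10 difference is the regression slope times the day-0 difference. For a day-0 difference of 1.96 standard errors, the day-0 SD cancels and the shift is r × 0.43 × 1.96 × √(2/100) = r × 0.1192.
- r = 0.3: 10^0.0358 = 1.09-fold.
- r = 0.5: 10^0.0596 = 1.15-fold.

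An imbalance this large or larger, in either direction, is expected in about 1 subset in 20. The adjusted ratio largely removes the shift.

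**Step 4. Would fold changes from day 0 do the same job?**
SAP 6.1.2 lists geometric mean fold changes between time points. If the SDs at the two times are equal (an assumption), the SD of a change is 0.43 × √(2(1 − r)). The detectable ratio of fold changes is then 1.74 at r = 0, 1.59 at r = 0.3 and 1.48 at r = 0.5. Below r = 0.5 this is less precise than the crude ratio, and it is never more precise than the covariate-adjusted one. No table shell shows an arm ratio of fold changes.

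**The case against.** The strongest reply is that the adjustment is already planned. Protocol 11.1.2 and 12.1.2 provide for covariate-adjusted normal-errors regression beside the GMT intervals. Protocol 9.2 and SAP 12.3 list day-0 titre, and SAP 3.0 refers back to the protocol's statistics section. In the SAP 12.3 list only crying and respiratory symptoms are marked as applying to the aerosol arm, which suggests that day-0 titre was meant for models with both arms. SAP 9.2 leaves the final table format open, so a missing column is not a missing analysis. The day-0 rows of Table 12.2.1.2 would also make an imbalance visible.

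Most of this stands. A reader might infer from the tables that the plan ignores baseline antibody, and the documents do not support that. What remains is that no passage defines an arm comparison of antibody level with day-0 titre in the model. Showing an imbalance in a separate row does not correct for it.

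Three further objections stand:
- The crude ratio is unbiased because allocation is randomised, and the stated target is met without adjustment.
- The gain depends on an unknown correlation. SAP 11.12.1 sets results at the PRNT lower limit to 10 and OD below 0.01 to 0.005. If many infants have such values at day 0, the correlation and the gain could be small.
- The remedy has limits. Site is constant within the Vadu subset. Day-0 PRNT is not assured outside Vadu. The Table 12.1.8 rows selected on day-91 OD are conditioned on a post-vaccination result, which baseline adjustment does not repair.

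**Conclusion.** The point holds as a minor matter of specification and precision in a secondary endpoint. The arm GMT ratios in Table 12.2.1.2, and the ratio for day-91 OD in all infants in Table 12.1.8, are crude. The plan has the log-antibody model and the day-0 covariate but does not combine them into an adjusted ratio.

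For the Vadu subset the detectable ratio would move from 1.48-fold to 1.45 if r = 0.3 or 1.40 if r = 0.5, with almost no change if r is 0.2 or less. These figures rest on the SAP's SD of 0.43 and 100 per arm, and on correlations that are assumed. No such figure can be given for Table 12.1.8, because the documents state no SD for log OD. That table covers about 800 per arm (1600 available in all), so less is at stake there.

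A reader might go further and conclude that the crude ratios are biased, or that the non-inferiority result or the sample size is in doubt. Neither follows. Randomisation protects the crude ratio in expectation, the primary analysis concerns seropositivity, and the stated detectable difference reproduces without adjustment.

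**What to change.** 1. **SAP 11.9:** add the child's own log10 day-0 value to the covariates of the normal-errors regression. State that the arm effect from this model will be reported as an adjusted GMT ratio.
2. **Table 12.2.1.2:** for each post-vaccination row, report as the main GMT comparison the AER/SC ratio with 95% CI from a linear model of log10 titre (or log10 OD) on arm, log10 day-0 value of the same assay, and age. Include no site term, since all these children are from Vadu.
3. **Table 12.1.8:** do the same for the day-91 OD row covering all infants only, with log10 day-0 OD, age and site. Leave the rows selected on OD as description.
4. Keep the raw GMTs and the day-0 rows as description.

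The cost is a sentence or two in SAP 11.9 and one added column in each of two tables. No further assays, visits or children are needed. The change should be fixed in the SAP before unblinding, so that the model is not chosen after the arm results are known.
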